3 INVESTIGATIONAL PLAN

3.1 Study Design and Duration

This is a Phase 3, randomized, open-label, three-arm study of nivolumab plus ipilimumab or nivolumab in combination with oxaliplatin plus fluoropyrimidine vs oxaliplatin plus fluoropyrimidine in subjects with previously untreated advanced or metastatic GC or GEJ cancer. The nivolumab plus ipilimumab arm is closed to enrollment as of 05-June-2018. Subjects enrolled in this arm prior to 05-June-2018 will continue to receive treatment with study drugs per protocol and the study data will remain blinded for the planned primary analysis.

The study will enroll subjects regardless the PD L1 expressing tumors.

The original study design (before Amendment 08) had two arms. After signing the informed consent form, and upon confirmation of the subject's eligibility, subjects were randomized in an open-label fashion (1:1 ratio) to either the nivolumab-plus-ipilimumab arm or the chemotherapy (XELOX or FOLFOX) arm.

Amendment 08 added a new, nivolumab-plus-chemotherapy (XELOX or FOLFOX) arm. The IRT switched to a 1:1:1 randomization at all the study participating sites.

Amendment 19 added approximately 300 subjects to the study; in total approximately 1649 subjects will be randomized. The nivolumab plus ipilimumab arm was closed to enrollment as of 05-June-2018. Subjects randomized to treatment in this arm prior to 05-June-2018 will continue to receive treatment with study drugs per protocol, and the study data will remain blinded for the planned primary analysis. Per Amendment 20, subjects will be randomized in an open-label fashion (1:1) to either the nivolumab-plus-chemotherapy (XELOX or FOLFOX) or the chemotherapy arm (XELOX or FOLFOX):

• Nivolumab-plus-Ipilimumab Arm: nivolumab 1 mg/kg administered IV over 30 minutes followed by ipilimumab 3 mg/kg administered IV over 30 minutes on Day 1 of each treatment cycle every 3 weeks for 4 doses (Cycles 1 to 4), followed by nivolumab 240 mg administered IV over 30 minutes on Day 1 of each treatment cycle every 2 weeks (Cycle 5 and beyond). Arm is closed to enrollment as of 05-June-2018.

• Nivolumab-plus-Chemotherapy Arm (XELOX or FOLFOX):

Nivolumab plus XELOX	Nivolumab plus FOLFOX		
Nivolumab 360 mg IV over 30 minutes on Day 1 of each treatment cycle, every 3 weeks	Nivolumab 240 mg IV over 30 minutes on Day 1 of each treatment cycle, every 2 weeks		
Oxaliplatin 130 mg/m ² IV on Day 1 of each treatment cycle + capecitabine 1000 mg/m ² orally twice daily (ie, 1000 mg/m ² in the morning and 1000 mg/m ² in the evening) on Days 1 to 14 of each treatment cycle, every 3 weeks	Oxaliplatin 85 mg/m² + leucovorin 400 mg/m² + fluorouracil 400 mg/m² IV on Day 1 of each treatment cycle, and fluorouracil 1200 mg/m² IV continuous infusion over 24 hours (or per local standard) daily on Days 1 and 2 of each treatment cycle, every 2 weeks		

or

• Chemotherapy Arm (XELOX or FOLFOX) :

XELOX	FOLFOX
Oxaliplatin 130 mg/m² IV on Day 1 of each treatment cycle + capecitabine 1000 mg/m² orally twice daily (ie, 1000 mg/m² in the morning and 1000 mg/m² in the evening) on Days 1 to 14 of each treatment cycle, every 3 weeks	Oxaliplatin 85 mg/m² + leucovorin 400 mg/m² + fluorouracil 400 mg/m² IV on Day 1 of each treatment cycle, and fluorouracil 1200 mg/m² IV continuous infusion over 24 hours (or per local standard) daily on Days 1 and 2 of each treatment cycle, every 2 weeks

Amendment 26 added approximately 356 subjects to the study; in total approximately 2005 subjects will be randomized. However, given the uncertainty about the CPS \geq 5 prevalence, the sample size may need to be further adjusted based on the monitoring of the prevalence to keep sample size for the primary population.

The treatment will be given until disease progression (PD) (unless treatment beyond progression is permitted, in nivolumab-plus-ipilimumab and nivolumab-plus-chemotherapy arms; see Section 4.5.1.6), unacceptable toxicity, maximum 24 months treatment duration or subject withdrawal of consent, whichever comes first.

Based on investigator judgment of benefit/risk, nivolumab 480 mg flat dose Q4W (IV over 30 minutes on Day 1 of each treatment cycle, Q4W) can be used as an option for those subjects who receive nivolumab treatment alone. For subjects in nivolumab-plus-chemotherapy arm, a 480 mg Q4W nivolumab treatment regimen will be permitted when all chemotherapy is discontinued and nivolumab is continued alone. Subjects must be in the study for a minimum of 6 months from Cycle 1, Day 1 before switching to 480 mg Q4W nivolumab.

Chemotherapy will be given as per the study dosing schedule.

[figure not shown]
Stratification factors:

- 1) PD-L1 status (≥ 1% vs < 1% [including indeterminate])*
- 2) Region (Asia vs US vs Rest of world [ROW])
- 3) ECOG performance status (0 vs 1).
- 4) Chemotherapy (XELOX vs FOLFOX)
- * During enrollment, the proportion of subjects with or without PD-L1 tumor expression will be monitored in pooled fashion, and may be re-assessed in case it does not reflect study assumptions (ie, subjects with PD-L1 tumor expression \geq 1% is approximately 40% of all comers).

Per Amendment 23, PD-L1 expression has incorporated CPS scoring for the analysis. However, the stratification factor of tumor proportion score (TPS) remains unchanged for consistency.

The study design schematic is presented in Figure 3.1-1.

Figure 3.1-1: Study Design Schematic

* Nivolumab + Ipilimumab arm is closed to enrollment as of 05-June-2018.

This study will consist of 3 phases: screening, treatment, and follow-up.

3.1.1 Screening Phase

- Begins by establishing the subject's initial eligibility and signing of the informed consent form (ICF).
- Subject is enrolled using the Interactive Response Technology (IRT) system.
- The choice of chemotherapy regimen XELOX or FOLFOX must be decided before contacting the IRT system for randomization.
- Subjects must have PD-L1 immunohistochemistry (IHC) testing, with evaluable results, performed by the central lab during the Screening period. Either a formalin-fixed, paraffinembedded (FFPE) tissue block or unstained tumor tissue sections, with an associated pathology report, must be submitted for biomarker evaluation prior to randomization. The tumor tissue sample may be fresh or archival if obtained within 6 months prior to randomization, and there can have been no systemic therapy (eg, adjuvant) given after the sample was obtained. Tissue must be a core needle biopsy, excisional or incisional biopsy. Fine needle biopsies are not considered adequate for biomarker review and randomization. Biopsies of bone lesions that do not have a soft tissue component or decalcified bone tumor samples are also not acceptable. If

insufficient tumor tissue is provided for analysis, acquisition of additional tumor tissue (block and/or slides) for the biomarker analysis is required.

Subject is assessed for study eligibility according to the inclusion (Section 3.3.1) and exclusion (Section 3.3.2) criteria. The detailed procedures are described in Table 5.1-1.

3.1.2 Treatment Phase

- Begins after contacting the IRT system for randomization.
- Per Amendment 20, subjects will be randomized in an open-label fashion (1:1) to either the nivolumab-plus-chemotherapy (XELOX or FOLFOX) or the chemotherapy arm (XELOX or FOLFOX).
- Administration of study treatment is to begin within 3 calendar days of randomization.
- The treatment phase ends when the subject is discontinued from study therapy (ie, PD, unacceptable toxicity, maximum 2 year treatment of nivolumab, or subject withdrawal of consent).
- Adverse event assessments should be documented at each clinic visit and Women of Child-bearing Potential (WOCBP) must have a pregnancy test every 4 weeks (± 7 days).
- Treated subjects will be evaluated for tumor assessments every 6 weeks (± 7 days) up to and including Week 48, then every 12 weeks (± 7 days) thereafter.
- Biomarker sampling will follow the protocol-defined schedule
- Patient-reported questionnaires EQ-5D-3L and FACT-Ga will be collected every 6 weeks.

Nivolumab-plus-Ipilimumab Arm: Closed to enrollment as of 05-June-2018.

- On the day of infusion, nivolumab is to be administered first. The second infusion will always be ipilimumab, and will start at least 30 minutes after completion of the nivolumab infusion.
- Treatment beyond initial, investigator-assessed, RECIST 1.1-defined progression is permitted if the subject has investigator-assessed clinical benefit and is tolerating treatment, as specified in Section 4.5.1.6.
- PK and IMG sampling data will be collected as indicated in Table 5.5-1.

Nivolumab-plus-Chemotherapy (XELOX or FOLFOX) Arm:

- On the day of infusion, nivolumab is to be administered first. The administration procedures of chemotherapy will follow local standards.
- Nivolumab is allowed to be administrated alone in case the chemotherapy has to be discontinued due to toxicity. Chemotherapy alone is also allowed to be administered in doublet or monotherapy in case nivolumab has to be discontinued due to unacceptable toxicity.
- Nivolumab treatment beyond initial, investigator-assessed, RECIST 1.1-defined progression is permitted if the subject has investigator-assessed clinical benefit and is tolerating treatment, as specified in Section 4.5.1.6. Chemotherapy alone is not allowed to treat beyond progression.
- PK and IMG sampling data will be collected as indicated in Table 5.5-2 (Nivolumab with XELOX) and Table 5.5-3 (Nivolumab with FOLFOX).
- No cross-over is allowed between XELOX and FOLFOX.

Chemotherapy Arm (XELOX or FOLFOX)

- The administration procedures will follow the local standards.
- No cross-over is allowed between XELOX and FOLFOX.

Study assessment data are to be collected as outlined in Table 5.1-2 (on-treatment assessments, nivolumab-plus-ipilimumab), Table 5.1-3 (on-treatment assessments, nivolumab-plus-chemotherapy), and Table 5.1-4 (on-treatment assessments, chemotherapy).

3.1.3 Follow-up Phase

- Begins when the decision is made to discontinue a subject from study therapy.
- After completion of the first 2 follow-up (FU) visits (30 days [± 7 days] from last dose and 84 days [± 7 days] from FU1), subjects will be followed by clinic visit or phone contact every 3 months (± 14 days) or more frequently as needed for survival status and subsequent anti-cancer therapy.
- Subjects who discontinue treatment for reasons other than PD will continue to have tumor assessments (until PD) every 6 weeks (± 7 days) up to and including Week 48, then every 12 weeks (± 7 days) thereafter.
- Subjects will be followed for drug-related toxicities until these toxicities resolve, return to baseline or are deemed irreversible. All toxicities will be documented for a minimum of 100 days after the last dose of study drug.
- Patient-reported questionnaires EQ-5D-3L, GaCS from the FACT-Ga, and the FACT-G7 will be collected every 3 months (± 14 days) via phone contact or in-person visit.
- The biomarker sampling will continue as per protocol defined schedule

Study follow-up assessment data are to be collected as outlined in Table 5.1-5.

The start of the trial is defined as the first visit for the first subject screened. End of trial is defined as the last visit or scheduled procedure shown in the Time & Events schedule for the last subject. Study completion is defined as the final date on which data for the primary endpoint was or is expected to be collected, if this is not the same.

3.2 Post-Study Access to Therapy

At the conclusion of the study, participants who continue to demonstrate clinical benefit will be eligible to receive BMS supplied study treatment for the maximum treatment duration allowed by the study protocol. Study treatment will be provided via an extension of the study, a rollover study requiring approval by responsible health authority and ethics committee or through another mechanism at the discretion of BMS. BMS reserves the right to terminate access to BMS supplied study drug if any of the following occur: a) the study is terminated due to safety concerns, b) development is terminated for other reasons, including but not limited to lack of efficacy and/or not meeting the study objectives, c) the subject can obtain medication from a government sponsored or private health program.

3.3 Study Population

For entry into the study, the following criteria must be met.

3.3.1 Inclusion Criteria

1. Signed Written Informed Consent

- a) Subjects must have signed and dated an IRB/IEC approved written informed consent form in accordance with regulatory and institutional guidelines. This must be obtained before the performance of any protocol-related procedures that are not part of normal subject care.
- b) Subjects must be willing and able to comply with scheduled visits, treatment schedule, laboratory tests and other requirements of the study.

2. Target Population

- a) All subjects must have inoperable, advanced or metastatic GC or GEJ or distal esophageal carcinoma and have histologically confirmed predominant adenocarcinoma. The documentation of GEJ involvement can include biopsy, endoscopy, or imaging.
- b) Subject must be previously untreated with systemic treatment (including HER 2 inhibitors) given as primary therapy for advanced or metastatic disease.
- c) Allowed Prior Therapies: Prior adjuvant or neoadjuvant chemotherapy, radiotherapy and/or chemoradiotherapy for GC or GEJ cancer are permitted as long as the last administration of the last regimen (whichever was given last) occurred at least 6 months prior to randomization. Palliative radiotherapy is allowed and must be completed 2 weeks prior to randomization.
- d) Subject must have at least one measurable lesion or evaluable disease by CT or MRI per RECIST 1.1 criteria; radiographic tumor assessment should be performed within 28 days prior to randomization.
- e) ECOG performance status score of 0 or 1 (Appendix 3).
- f) Tumor tissue must be provided for biomarker analyses. In order to be randomized, a subject must have an evaluable PD-L1 expression classification (≥ 1% or < 1%, or indeterminate) as determined by the central lab. Subjects with non-evaluable results will not be allowed to be randomized. Either a formalin-fixed, paraffin-embedded (FFPE) tissue block or unstained tumor tissue sections, with an associated pathology report, must be submitted for biomarker evaluation prior to randomization. The tumor tissue sample may be fresh or archival if obtained within 6 months prior to randomization, and there can have been no systemic therapy (eg, adjuvant) given after the sample was obtained. Tissue must be a core needle biopsy, excisional or incisional biopsy.
- g) Subject re-enrollment: this study permits the re-enrollment of a subject who has discontinued the study as a pre-treatment failure (ie, subject has not been randomized). If re-enrolled, the subject must be re-consented.
- h) Screening laboratory values must meet the following criteria:

i) WBC $\geq 2000/uL$

ii) Neutrophils ≥ 1500/uL

iii) Platelets $\geq 100 \text{ x } 10^3/\text{uL}$

iv) Hemoglobin $\geq 9.0 \text{ g/dL}$

- v) Serum albumin $\geq 3.0 \text{ g/dL}$
- vi) Serum creatinine ≤ 1.5 x ULN or calculated creatinine clearance > 50 mL/min (using the Cockcroft-Gault formula)

Female CrCl = (140- age in years) x weight in kg x 0.85 72 x serum creatinine in mg/ dL

Male CrCl = (140- age in years) x weight in kg x 1.00

72 x serum creatinine in mg/ dL

- vii) AST $\leq 3.0 \text{ x ULN (or } \leq 5.0 \text{ x ULN if liver metastases are present)}$
- viii) ALT $\leq 3.0 \text{ x ULN (or } \leq 5.0 \text{ x ULN if liver metastases are present)}$
- ix) Total Bilirubin ≤ 1.5 x ULN (except subjects with Gilbert Syndrome who must have a total bilirubin level of ≤ 3.0 x ULN)

Note: For subjects with hemoglobin ≥ 8.0 g/dL, blood transfusion is allowed and must be completed at least 72 hours prior to randomization. The repeated hemoglobin value ≥ 9.0 g/dL must be verified prior to randomization.

3. Age and Reproductive Status

- a) Males and Females, ≥ 18 years of age
- b) Women of childbearing potential (WOCBP) must have a negative serum or urine pregnancy test (minimum sensitivity 25 IU/L or equivalent units of HCG) within 24 hours prior to the start of study drug.
- c) WOCBP randomized to the nivolumab-plus-ipilimumab arm or the nivolumab-plus-chemotherapy arm must agree to follow instructions for method(s) of contraception for the duration of study treatment and 5 months after the last dose of study treatment (i.e., 30 days [duration of ovulatory cycle] plus the time required for the investigational drug to undergo approximately five half-lives).
- d) Males randomized to the nivolumab plus ipilimumab arm or the nivolumab-plus-chemotherapy arm and who are sexually active with WOCBP must agree to follow instructions for method(s) of contraception and fetal protection for the duration of study treatment and 7 months after the last dose of study treatment (i.e., 90 days [duration of sperm turnover] plus the time required for the investigational drug to undergo approximately five half-lives). In addition, male subjects must be willing to refrain from sperm donation during this time.
- e) WOCBP randomized to the chemotherapy arm must agree to follow instructions for method(s) of contraception for a period of 30 days (duration of ovulatory cycle) plus the time required for the investigational drug to undergo at least 5 half-lives. WOCBP randomized to the chemotherapy arm should use an adequate method to avoid pregnancy for approximately 4.5 months (ie, 30 days plus 98 days) after the last dose of investigational drug.

- f) Males randomized to the chemotherapy arm and who are sexually active with WOCBP must agree to follow instructions for methods of contraception for a period of 90 days (duration of sperm turnover) plus the time required for the investigational drug to undergo at least 5 half-lives. Males randomized to the chemotherapy arm and who are sexually active with WOCBP should use an adequate method to avoid pregnancy for approximately 6 months (ie, 90 days plus 98 days) after the last dose of investigational drug. In addition, male subjects must be willing to refrain from sperm donation during this time.
- g) Azoospermic males are exempt from contraceptive requirements unless the potential exists for fetal toxicity due to study drug being present in seminal fluid, even if the subject has undergone a successful vasectomy or if the partner is pregnant. WOCBP who are continuously not heterosexually active are also exempt from contraceptive requirements, but still must undergo pregnancy testing as described in this section.
- h) Women must not be breastfeeding.

Investigators shall counsel WOCBP and male subjects who are sexually active with WOCBP on the importance of pregnancy prevention and the implications of an unexpected pregnancy and when applicable, the potential of fetal toxicity occurring due to transmission of study drug, present in seminal fluid, to a developing fetus, even if the subject has undergone a successful vasectomy or if the partner is pregnant. Investigators shall advise on the use of highly effective methods of contraception (Appendix 2), which have a failure rate of < 1% when used consistently and correctly.

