APPENDIX 2 WOMEN OF CHILDBEARING POTENTIAL DEFINITIONS AND METHODS OF CONTRACEPTION

DEFINITIONS

Woman of Childbearing Potential (WOCBP)

A woman is considered fertile following menarche and until becoming post-menopausal unless permanently sterile. Permanent sterilization methods include hysterectomy, bilateral salpingectomy, and bilateral oophorectomy.

Women in the following categories are not considered WOCBP

- Premenarchal
- Premenopausal female with 1 of the following:
 - Documented hysterectomy
 - Documented bilateral salpingectomy
 - Documented bilateral oophorectomy

Note: Documentation can come from the site personnel's review of the participant's medical records, medical examination, or medical history interview.

- Postmenopausal female
 - A postmenopausal state is defined as 12 months of amenorrhea in a woman over age 45 years in the absence of other biological or physiological causes. In addition, females under the age of 55 years must have a serum follicle stimulating hormone, (FSH) level > 40 mIU/mL to confirm menopause.

CONTRACEPTION GUIDANCE FOR FEMALE PARTICIPANTS OF CHILD BEARING POTENTIAL

One of the highly effective methods of contraception listed below is required during study duration and until the end of relevant systemic exposure, defined as 5 months after the end of study treatment.

Local laws and regulations may require use of alternative and/or additional contraception methods.

Highly Effective Contraceptive Methods That Are User Dependent

Failure rate of <1% per year when used consistently and correctly.^a

- Combined (estrogen- and progestogen-containing) hormonal contraception associated with inhibition of ovulation^b
 - oral
 - intravaginal
 - transdermal
- Progestogen-only hormonal contraception associated with inhibition of ovulation^b
 - oral
 - injectable

Highly Effective Methods That Are User Independent

- Implantable progestogen-only hormonal contraception associated with inhibition of ovulation ^b
- Intrauterine device (IUD)^c
- Intrauterine hormone-releasing system (IUS)^c
- Bilateral tubal occlusion
- Vasectomized partner

A vasectomized partner is a highly effective contraception method provided that the partner is the sole male sexual partner of the WOCBP and the absence of sperm has been confirmed. If not, an additional highly effective method of contraception should be used.

Sexual abstinence

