Male participants with female partners of childbearing potential are eligible to participate if they agree to the following during the treatment and until the end of relevant systemic exposure.

- Inform any and all partner(s) of their participation in a clinical drug study and the need to comply with contraception instructions as directed by the investigator.
- Male participants are required to use a condom for study duration and until the end of relevant systemic exposure defined as 7 months after the end of treatment in the male participant.
- Female partners of males participating in the study to consider use of effective methods of contraception until the end of relevant systemic exposure, defined as 7 months after the end of treatment in the male participant.
- Male participants with a pregnant or breastfeeding partner must agree to remain abstinent from penile vaginal intercourse or use a male condom during each episode of penile penetration during the treatment and until 7 months after the end of treatment.
- Refrain from donating sperm for the duration of the study treatment and for 7 months after the end of treatment.

COLLECTION OF PREGNANCY INFORMATION

Guidance for collection of Pregnancy Information and outcome of pregnancy on the Pregnancy Surveillance Form is provided in Section 6.4.

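### For the chemotherapy arm, criteria 3e and 3f set shorter post-treatment contraception periods than Appendix 2 (about 4.5 and 6 months against 5 and 7), and nothing says which governs

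*Protocol*

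**What the plan says.** Section 3.3.1 of the protocol, under Age and Reproductive Status, sets contraception periods by arm.

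- **Nivolumab-containing arms (3c, 3d).** Women of childbearing potential must follow contraception instructions "for the duration of study treatment and 5 months after the last dose of study treatment". For men the post-treatment period is 7 months.
- **Chemotherapy arm, women (3e).** They "should use an adequate method to avoid pregnancy for approximately 4.5 months (ie, 30 days plus 98 days" after the last dose.
- **Chemotherapy arm, men (3f).** They "should use an adequate method to avoid pregnancy for approximately 6 months (ie, 90 days plus 98 days) after the last dose". The criterion then adds: "In addition, male subjects must be willing to refrain from sperm donation during this time".

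Appendix 2 sets periods without naming an arm.

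- **Women.** A highly effective method is "required during study duration and until the end of relevant systemic exposure, defined as 5 months after the end of study treatment".
- **Men.** Those with partners of childbearing potential "are eligible to participate if they agree to the following during the treatment and until the end of relevant systemic exposure". The list that follows includes this duration, counted from when treatment stops: "Male participants are required to use a condom for study duration and until the end of relevant systemic exposure defined as 7 months after". The same 7 months is given for sperm donation.

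Section 3.3.1 refers to Appendix 2 in its counselling paragraph: "Investigators shall advise on the use of highly effective methods of contraception (Appendix 2". That reference concerns methods. It says nothing about duration or about which text takes precedence.

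**The concern.** Two operative texts give different durations for the same subjects. Appendix 2 is more than background: it calls a method required for women and words the male obligations as a condition of taking part. Oxaliplatin, capecitabine, fluorouracil and leucovorin are all listed as investigational products in Section 4.1, so study treatment in Appendix 2 naturally covers the control arm. A chemotherapy-arm man who agrees to about 6 months meets 3f but not Appendix 2.

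The instruction guards against fetal exposure. One site could read 3e/3f and another Appendix 2, and each could point to the protocol for support. What is at stake is a few weeks of contraception and sperm-donation restraint in the control arm.

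**Working it through.** No power, alpha or sample-size figure is involved. The check sets the texts side by side and converts months to days.

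**Inputs**

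- Criterion 3e, women: about 4.5 months, also given as 30 plus 98 days.
- Criterion 3f, men: about 6 months, also given as 90 plus 98 days.
- Appendix 2: 5 months for women and 7 months for men.
- 1 month = 30.4375 days (SAP Section 9, Conventions). This is an analysis convention, used here only to put the periods on one scale.
- Last dose (3e/3f) and end of treatment (Appendix 2) are taken as the same starting point.

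**Periods in days**

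- Women, 3e: day count 30 + 98 = 128; month label 4.5 × 30.4375 = 137.0.
- Women, Appendix 2: 5 × 30.4375 = 152.2.
- Men, 3f: day count 90 + 98 = 188; month label 6 × 30.4375 = 182.6.
- Men, Appendix 2: 7 × 30.4375 = 213.1.

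**Gap = Appendix 2 period minus criterion period**

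| | By month label | By day count |
|---|---|---|
| Women | 152.2 − 137.0 = 15.2 days | 152.2 − 128 = 24.2 days |
| Men (contraception and sperm donation) | 213.1 − 182.6 = 30.4 days (unrounded inputs) | 213.1 − 188 = 25.1 days |

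The gap is thus about 15 to 24 days for women and 25 to 30 days for men, or 15 to 30 days overall. In weeks, 15.2 / 7 = 2.2 and 30.4 / 7 = 4.3. The month labels in 3e/3f are approximate, so label and day count are used as the two ends of a range and not as a further discrepancy.

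**Is there a rule that settles it?**

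- Appendix 2 matches 3c and 3d exactly, and those criteria cover only the nivolumab-containing arms.
- Neither Appendix 2 heading limits the guidance to those arms.
- The counselling paragraph in 3.3.1 sends the investigator to Appendix 2 for methods only.
- The remark in Appendix 2 about local laws concerns alternative or additional methods and does not rank the two sections.

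No sentence in either document says which period governs for the chemotherapy arm.

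**The case against.** The strongest answer is that ordinary reading resolves the difference. Criteria 3e and 3f name the chemotherapy arm, whereas Appendix 2 is headed as guidance and ties its period to the end of relevant systemic exposure. Its 5 and 7 months are the nivolumab-arm periods. Specific criteria are normally read ahead of general guidance, and the separate day counts suggest that a shorter control-arm period was deliberate. Nor do the texts pull in opposite directions: a site that uses 5 and 7 months complies with both. The eligibility wording appears only in the male section of Appendix 2. Accrual ended in May 2019, before this protocol version of 16 September 2019, so nobody is newly screened against these criteria.

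Most of this stands and keeps the point small. It does not remove it, because the intended reading has to be inferred, and Appendix 2 still says that a method is required for 5 months and makes 7 months a condition for men.

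Three stronger readings are tempting, and the documents support none of them.

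- **That the shorter period is unsafe.** Sections 1.4.2.1 and 1.4.2.2 give half-lives for nivolumab and ipilimumab only. There is none for the chemotherapy drugs against which to judge 128 or 188 days.
- **That sites have in fact given different instructions.** Consent pages are not in the published text, so what subjects were told cannot be seen.
- **That the disputed days are left unprotected because Table 5.1-5 schedules a follow-up pregnancy test only at the first follow-up visit.** That schedule applies to every arm, including those with no discrepancy, so it is not a consequence of this one. Investigator counselling also applies throughout.

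**Conclusion.** The inconsistency is real and minor. For chemotherapy-arm subjects the protocol gives two post-treatment periods that differ by roughly 15 to 30 days, for women and for men, with the male difference extending to sperm donation. No text ranks them. The size rests on a 30.4375-day month and on a common starting point for both periods. The number of subjects affected is not given; it can include only chemotherapy-arm subjects still on treatment or within the post-treatment window. No harm is shown.

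**What to change.** Make the two texts agree, in one of two ways.

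1. **Set 3e and 3f to 5 months for women and 7 months for men, including sperm donation.** This is the conservative choice because it meets both existing texts. It costs chemotherapy-arm subjects about 2 to 4 more weeks of contraception.
2. **If the sponsor confirms the shorter chemotherapy-arm period,** limit the 5- and 7-month periods in Appendix 2 to the nivolumab-containing arms, and state there the 128-day (women) and 188-day (men) periods for the chemotherapy arm.

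Whichever is chosen, send a short letter to sites with chemotherapy-arm subjects still on treatment or in the post-treatment window, saying which period applies. Apart from the extra weeks under the first option, the cost is protocol wording and that letter.
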